2.3.3 Anti-alirocumab antibody population

The anti-alirocumab antibody (ADA) analyses in the OLDFI period and in the OLDFI/OLE combined period will be performed on all included and treated patients (safety population) with a blood sample on Week 0 (baseline) and at least one evaluable blood sample for antibodies post first IMP injection and up to the end of OLDFI period for patients not entering into OLE period, or up to end of OLE for patients proceeding into OLE period.

2.3.4 Pharmacokinetics population

The PK analysis in the OLDFI period will be performed on all included and treated patients (safety population) with at least one evaluable PK sample post first OLDFI IMP injection and up to the end of OLDFI period or first OLE IMP injection for patients proceeding into OLE period.

2.4 STATISTICAL METHODS

Statistical results will be presented for OLDFI period and for the OLDFI/OLE combined period with the exception of PK only assessed during OLDFI period.

For the OLDFI period, results will be presented by cohort and alirocumab dose group within each cohort and overall for demographic and baseline characteristics.

For Cohorts 1 to 3, two separate analyses will be performed for the OLDFI/OLE combined period:

- The first analysis will be truncated at the time before the switch to Phase 3 dose (s). This analysis will be presented by cohort and alirocumab dose group within each cohort;
- The second analysis will include data from the switch of Phase 3 dose(s) up to the end of OLE period and will be presented using selected Phase 3 doses regardless of doses previously received.

For Cohort 4, a single analysis will be performed for the OLDFI/OLE combined period since the patients from Cohort 4 who will enter the OLE phase will continue on their doses from main phase.

All summary tables will be provided for OLDFI period and for the combined analysis truncated at the time of the switch to Phase 3 dose (s) for Cohorts 1 to 3. For the analyses of the data from the switch, listings may be preferred to summary tables depending on the duration of follow-up and the amount of data post-switch.

2.4.1 Demographics and baseline characteristics

Parameters described in [Section 2.1.1](#) will be summarized in patients included and treated (ie, safety population) according to the alirocumab dose group allocated by IVRS.

Continuous data will be summarized using the number of available data, mean, SD, median, minimum and maximum. First quartile (Q1) and third quartile (Q3) will be also provided for baseline lipid parameters. Categorical and ordinal data will be summarized using the number and percentage of patients.

All reported patient's medical and surgical history will be presented by primary SOC and HLT. The tables will be sorted by SOC internationally agreed order and decreasing frequency of HLT based on the incidence in the whole population (all cohorts combined). In addition all medical history of specific interest (see [Section 2.1.1](#)) will also be presented.

2.4.2 Prior or concomitant medications

The prior, concomitant and post-treatment medications will be presented for the safety population.

Medications will be summarized according to the WHO-DD dictionary, considering the first digit of the anatomical therapeutic chemical (ATC) class (anatomic category) and the first 3 digits of the ATC class (therapeutic category). All ATC codes corresponding to a medication will be summarized, and patients will be counted once in each ATC category (anatomic or therapeutic) linked to the medication. Therefore patients may be counted in several categories for the same medication.

The table for prior medications will be sorted by decreasing frequency of ATC followed by therapeutic class based on the overall incidence across alirocumab dose groups (all groups combined). In case of equal frequency across anatomic or therapeutic categories, alphabetical order will be used.

The tables for concomitant and post-treatment medications will be sorted by decreasing frequency of ATC followed by therapeutic class based on the overall incidence across alirocumab doses groups from the Cohort 4 (all doses combined). In case of equal frequency across anatomic or therapeutic categories, alphabetical order will be used.

In addition, concomitant LMT and non-statins LMT medications will be summarized by pre-specified categories, chemical class or therapeutic class and standardized medication name.

LMT (statins and other LMTs) use after enrollment will be summarized over time during OLDFI period graphically by LMTs intensity at enrollment using the following categories:

- Statin
- Only LMT other than statin
- No LMT

The LMTs intensity at enrollment is defined as:

- Statin
- Only LMT other than statin

2.4.3 Extent of investigational medicinal product exposure and compliance

The extent of IMP exposure and compliance will be summarized for the safety population using as-treated alirocumab dose group.

2.4.3.1 Extent of investigational medicinal product exposure

The total exposure to IMP will be assessed using the following parameters:

- Duration of OLDFI IMP injection exposure in weeks defined as (date of last OLDFI IMP injection – date of first OLDFI IMP injection + 14 days)/7 (for Cohorts 1& 2) or (date of last OLDFI IMP injection – date of first OLDFI IMP injection + 28 days)/7 (for Cohorts 3 & 4), regardless of unplanned intermittent discontinuations.
- The total number of OLDFI IMP injections by patient.
- For Cohorts 1 to 3, and for the OLDFI/OLE combined period the following parameters will be derived up to, and post switch of dose:
 - Duration of OLDFI/OLE combined period IMP injection exposure up to the switch to Phase 3 doses in weeks, defined as (date of last IMP injection up to the switch – date of first IMP injection + 14 days)/7 (for Cohorts 1& 2) or (date of last IMP injection up to the switch – date of first IMP injection + 28 days)/7 (for Cohorts 3 & 4), regardless of unplanned intermittent discontinuations.
 - Duration of IMP injection exposure post switch in weeks, defined as: (date of last IMP injection +14 – date of first IMP injection post switch)/7, regardless of intermittent discontinuations.
 - Total number of OLDFI/OLE combined period IMP injections up to, and post switch of dose.
- For Cohort 4, and for the OLDFI/OLE combined period, the following parameters will be derived:
 - Duration of OLDFI/OLE combined period IMP injection exposure in weeks, defined as (date of last IMP injection – date of first IMP injection + 28 days)/7, regardless of unplanned intermittent discontinuations.
 - Total number of OLDFI/OLE combined period IMP injections.
- For duration of IMP injection exposure calculation, see [Section 2.5.3](#) for calculation in case of missing or incomplete data. Non-integer values will be rounded to one decimal place.

Duration of OLDFI IMP exposure will be summarized descriptively as a quantitative variable (number, mean, SD, median, minimum, and maximum) and categorically using the following categories: ≥ 1 day to <1 week, ≥ 1 to <3 weeks, ≥ 3 to <5 weeks, ≥ 5 to <7 weeks, ≥ 7 to <9 weeks, ≥ 9 to <11 weeks, ≥ 11 weeks.

Duration of OLDFI/OLE combined period IMP injection exposure will be summarized descriptively as a quantitative variable (number, mean, SD, median, minimum, and maximum) and categorically using the following categories: ≥ 1 day to <1 week, ≥ 1 to <3 weeks, ≥ 3 to <5 weeks, ≥ 5 to <7 weeks, ≥ 7 to <24 weeks, ≥ 24 to <52 weeks, ≥ 52 to <78 weeks, ≥ 78 to <104 weeks, ≥ 104 to <130 weeks, ≥ 130 weeks. In addition, cumulative exposure in patient-years will be provided.

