- Cohorts 1 and 2 (Q2W): Alirocumab injections will be prepared from vials by the pharmacist (or equivalent). Detailed instructions on preparation of injections from vials will be provided in a separate document. Alirocumab injections will be administered at Weeks 0, 2, 4, and 6. The Weeks 0 and 4 alirocumab injections will be administered at the clinical site by the site staff. The Weeks 2 and 6 alirocumab injections will be administered at the clinical site by the site staff or at the patient's home by a health care professional, depending upon local arrangements and preferences of the investigator/patient.
- Cohort 3 (Q4W): Alirocumab injections will be prepared from vials by the pharmacist (or equivalent). Detailed instructions on preparation of injections from vials will be provided in a separate document. Alirocumab injections will be administered at Weeks 0 and 4 at the clinical site by the site staff.
- Cohort 4 (Q4W): Alirocumab injections will be administered with prefilled syringes. Alirocumab injections will be administered Week 0, Week 4, and Week 8 at the clinical site by site staff.
- The lipid results from specimens obtained during the open-label dose finding treatment period will be masked for the clinical site/Investigator and patients. No attempts should be made by the investigator or patient to routinely have the patient's lipid values independently evaluated after entry into the open-label dose finding treatment period and until the final follow-up visit for Cohort 1, Cohort 2, and Cohort 3, and entry into the OLE period for Cohort 4. The sponsor and the DMC will closely monitor the lipid results during the 8-week open-label dose finding treatment period. If any safety concerns are noted during this period, including very low LDL-C levels (ie, LDL-C <50 mg/dL [1.30 mmol/L] on one or more occasion), then appropriate action will be taken by the Sponsor in consultation with the DMC.

Follow-Up Period, only for Cohorts 1 to 3:

- A follow-up period (off treatment) of 6 (Cohort 3) or 8 weeks (Cohorts 1 and 2) after the end of open-label dose finding treatment period visit. For these 3 cohorts, the final follow-up visit corresponds to 10 weeks after the last alirocumab injection administered during the open-label dose finding treatment period, since the last injection for Cohorts 1 & 2 is Week 6 and for Cohort 3 it is Week 4.

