8.1.2 Timing of administration

During the main dose finding treatment period the first alirocumab injection for each cohort will start at Week 0 (after each respective screening period and DMC agreement for Cohorts 2 and 3) as soon as possible after the call for inclusion using the treatment kit number provided by the IRT according to cohort number and body weight. The first injection after call for inclusion will be done at the site by the investigator staff. Patients will be monitored at the investigational site for at least 30 minutes after this first injection.

The investigator staff will administer subsequent injections on site at the clinic, according to the dosing schedule at approximately the same time of the day. On days where the clinic study visit coincides with dosing, the dose of study drug will be administered after all study assessments have been performed and all laboratory samples (including PK) collected. For visits where home injection is allowed, the health care professional will administer the injection at the patient's home, as described in the relevant manuals.

During the main dose finding treatment period, alirocumab will be administered subcutaneously every 2 weeks or every 4 weeks at approximately the same time of the day; however it is acceptable to have a window period of ± 3 days.

Follow-up period during the main phase without treatment

No alirocumab administration between W8 and W16 for Cohort 1.

No alirocumab administration between W8 and W16 for Cohort 2.

No alirocumab administration between W8 and W14 for Cohort 3.

There is no follow up period for Cohort 4.

During the open-label extension period for Cohorts 1 & 2 the first injection administration will start at Week 16 after the last injection administration at Week 6 (ie, 10 weeks after the last administration of alirocumab. The treatment kit(s) number(s) will be provided by IRT according to the last dose administered in Cohort1/Cohort 2. The first injection of the extension period will be done at the site by the investigator staff. If the self-injections by patient or another designated person (such as parent, nurse, etc.) are decided during the extension period a training injection should be planned 2 weeks before the first self-injection, under direct site staff supervision.

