For Cohorts 1- 3, the initial dose of alirocumab that will be administered during the extension phase, will be the continuation of same doses/regimens administered during the main phase up to the time when the final optimal doses for the Phase 3 study are selected and prefilled syringes

available. Then these final optimal doses will be administered to all patients during the extension phase, based on their body weight at the time of dose change.

For Cohort 4, if patients enter the OLE phase, patients will continue on their doses from the main phase.

At the end of each study phase, patients are to be followed 10 weeks after last alirocumab injection on site (for main phase, only for Cohorts 1-3 as this follow up period doesn't apply for Cohort 4) or by phone (for extension phase, for all cohorts). Patients with any adverse event (AE) should be followed until resolution, stabilization, or death, as specified in the protocol.

Approximately 40 patients (10 patients per cohort) were to be enrolled from approximately 28 sites.

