2.4.3.2 Compliance

Compliance for the open-label dose finding treatment period (OLDFI) will be assessed using the following parameters:

- The mean injection frequency of IMP OLDFI injections will be defined for each patient as the average number of days between 2 consecutive OLDFI injections, that is: (last OLDFI injection date – first OLDFI injection date)/(number of OLDFI injections -1) for patients receiving at least 2 OLDFI injections.
- The overall compliance for OLDFI injections will be defined for each patient as: 100- (%days with under-planned dosing + %days with above-planned dosing). Under-planned and above-planned dosing will be defined as follows, considering that injections should be performed every 2 weeks or every 4 weeks (± 3 days as per protocol):
 - The % days with under-planned dosing will be defined for each patient from Cohorts 1 & 2 as the number of days with no injection administered within the previous 17 days divided by the duration of IMP injection exposure in days. For example if a patient takes a dose 18 days after his/her previous injection, then 1 day is counted as a day under-planned dosing.
 - The % days with under-planned dosing will be defined for each patient from Cohorts 3 & 4 as the number of days with no injection administered within the previous 31 days divided by the duration of IMP injection exposure in days. For example if a patient takes a dose 32 days after his/her previous injection, then 1 day is counted as a day under-planned dosing.
 - The % days with above-planned dosing will be defined for each patient from Cohorts 1 & 2 as the number of days with more than one injection administered within the 11 days before divided by the duration of IMP injection exposure in days. For example if a patient takes a dose 9 days after his/her previous injection, then 2 days are counted as days above-planned dosing.
 - The % days with above-planned dosing will be defined for each patient from Cohorts 3 & 4 as the number of days with more than one injection administered within the 25 days before divided by the duration of IMP injection exposure in days. For example

if a patient takes a dose 23 days after his/her previous injection, then 2 days are counted as days above-planned dosing.

For the OLDFI/OLE combined period, only mean injection frequency will be assessed:

- For Cohorts 1 to 3, the mean injection frequency will be defined for each patient up to, and post switch of dose :

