 - Up to the switch of dose, the average number of days between 2 consecutive injections is defined as (last injection date up to the switch – first injection date)/(number of injections up to the switch -1) for patients receiving at least 2 injections;
 - Post switch of dose, the average number of days between 2 consecutive injections is defined as (last injection date– first injection date post switch)/(number of injections post switch -1) for patients receiving at least 2 injections;
- For Cohort 4, the mean injection frequency will be defined for each patient for the entire period (no switch is planned for these patients):
 - The average number of days between 2 consecutive injections, defined as: (last injection date– first injection date)/(number of injections -1) for patients receiving at least 2 injections;

These parameters will be summarized descriptively (N, Mean, SD, Median, Minimum and Maximum).

The percentage of patients whose overall compliance is <80% will be also summarized as well as numbers and percentages of patients with 0%, >0% and $\leq 5\%$, >5% and $\leq 10\%$, >10% and $\leq 20\%$, and >20% days with above-planned dosing and numbers and percentages of patients with 0%, >0% and $\leq 5\%$, >5% and $\leq 10\%$, >10% and $\leq 20\%$, and >20% days with under-planned dosing.

According to protocol, cases of overdose are reported in the AE e-CRF pages and will be described in the AE analysis (see [Section 2.1.4.1](#) and [Section 2.4.5.1](#)). More generally, dosing irregularities will be listed in [Section 2.2.1](#).

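### Combined pre-switch exposure and mean injection interval for Cohorts 1 to 3 run across the planned 10-week injection-free gap, overstating exposure by a nominal 8 or 6 weeks per affected patient

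*SAP*

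**What the plan says.** SAP 2.4.3.1 gives, for Cohorts 1 to 3, the "Duration of OLDFI/OLE combined period IMP injection exposure up to the switch to Phase 3 doses in weeks, defined as" the date of the last injection up to the switch minus the date of the first injection, plus 14 days (Cohorts 1 and 2) or 28 days (Cohort 3), over 7. This applies "regardless of unplanned intermittent discontinuations". The result is summarized in categories and added up: "In addition, cumulative exposure in patient-years will be provided".

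SAP 2.4.3.2 treats compliance in the same way. "Up to the switch of dose, the average number of days between 2 consecutive injections is defined as" last minus first injection date over the number of injections minus one. It is the only compliance measure for this period: "For the OLDFI/OLE combined period, only mean injection frequency will be assessed".

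The schedule contains a planned break. Protocol 6.1 describes "A follow-up period (off treatment) of 6 (Cohort 3) or 8 weeks (Cohorts 1 and 2". Protocol 8.1.2 states for Cohorts 1 and 2 that in the extension "the first injection administration will start at Week 16 after the last injection administration at Week 6". For Cohort 3 the corresponding weeks are 14 and 4. SAP 1.1 says that the initial extension dose in Cohorts 1 to 3 "will be the continuation of same doses/regimens administered during the main phase up to the time when the final optimal doses" are selected and prefilled syringes are available. The first extension injections therefore normally count as pre-switch.

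**The concern.** A first-to-last formula measures time on treatment only if dosing is meant to be continuous between the two dates. Here it is not. Neither formula has a term for the planned gap, and the conventions in SAP 2.5.1 and 2.5.3 add none.

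Three outputs are affected: the exposure duration and its categories, the cumulative patient-years, and the mean injection interval. The interval matters most, because it is presented as compliance and reports a perfectly adherent patient as under-dosed. The cohorts also stop being comparable. Cohort 4 moves from its Week 8 injection to Week 12 with no break, so the same formula is correct there.

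A lesser consequence has the same cause. The combined treatment period (SAP 2.1.4) and the combined efficacy treatment period (SAP 2.4.4.2.4) are also unbroken spans. Visit 8 vital signs, laboratory tests repeated after a Week 8 abnormality, and lipids are all taken before the first extension dose, about 10 weeks after the previous injection. All are nonetheless counted as on-treatment.

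**Working it through.** **Inputs.** Main-phase injections are at Weeks 0, 2, 4 and 6 (Cohorts 1 and 2) or Weeks 0 and 4 (Cohort 3), from Protocol 6.1. The first extension injection is at Week 16 or Week 14 (Protocol 8.1.2). The tail added after the last dose is 14 or 28 days (SAP 2.4.3.1). Let k be the number of pre-switch extension doses, given on schedule. The documents do not give k.

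**Reproducing the plan's own figure.** Within the main phase the formula works: (42 + 14)/7 = 8 weeks, and (28 + 28)/7 = 8 weeks. Both match the planned 8-week treatment period. The gap is 16 − 6 = 10 weeks, or 14 − 4 = 10 weeks.

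**Exposure.**
- Cohorts 1 and 2: the last injection is at Week 14 + 2k, so the SAP formula gives 16 + 2k weeks. The two segments add up to 8 + 2k. Excess: 8 weeks (10 − 2).
- Cohort 3: the last injection is at Week 10 + 4k, so the SAP formula gives 14 + 4k weeks. The two segments add up to 8 + 4k. Excess: 6 weeks (10 − 4).

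The excess does not depend on k.

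**Mean interval for an on-schedule patient.**
- Cohorts 1 and 2: 7(14 + 2k)/(k + 3) = 14 + 56/(k + 3) days, against 14.
- Cohort 3: 7(10 + 4k)/(k + 1) = 28 + 42/(k + 1) days, against 28.

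| Cohort | k | SAP exposure (weeks) | By segment (weeks) | Excess | SAP interval (days) |
|---|---|---|---|---|---|
| 1 and 2 | 1 | 18 | 10 | 80% | 28.0 |
| 1 and 2 | 4 | 24 | 16 | 50% | 22.0 |
| 1 and 2 | 12 | 40 | 32 | 25% | 17.7 |
| 3 | 1 | 18 | 12 | 50% | 49.0 |
| 3 | 3 | 26 | 20 | 30% | 38.5 |
| 3 | 12 | 62 | 56 | 11% | 31.2 |

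Some patients change exposure category. At k = 4 (Cohorts 1 and 2) or k = 3 (Cohort 3) a patient moves from the 7-to-24-week band to the 24-to-52-week band.

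**Windows.** A ±3-day injection window and the ±7-day Visit 8 window give (56 ± 10)/7 = 6.6 to 9.4 weeks and (42 ± 10)/7 = 4.6 to 7.4 weeks. These are not hard limits, because Protocol 8.1.2 also allows delayed injections.

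**Patient-years.** Protocol 4 reports 31 patients in Cohorts 1 to 3. Assume that all enter the extension before the switch:
- 20 in Cohorts 1 and 2, 11 in Cohort 3: 20×8 + 11×6 = 226 weeks = 4.33 years.
- 21 and 10: 21×8 + 10×6 = 228 weeks = 4.37 years.
- 21 and 10 at the outer edge of the windows: (21×66 + 10×52)/7 = 272 weeks, about 5.2 years.

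**First-step analysis.** SAP 3 uses the cut-off date as the last injection date for ongoing patients. If the cut-off is C days after the first injection and falls in the extension, the Cohort 1 and 2 excess is (C + 14) − [56 + (C − 112 + 14)] = 56 days, still 8 weeks. For Cohort 3 it is (C + 28) − [56 + (C − 98 + 28)] = 42 days, still 6 weeks.

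**On-treatment values.** The main-phase treatment period ends nominally at Week 9 in all three cohorts (Week 6 + 21 days, or Week 4 + 35 days). Visit 8 at Week 16 or 14 is 7 or 5 weeks later, yet lies inside both combined periods.

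**The case against.** The best defence is that first-to-last plus one dosing interval is an explicit calendar convention, that alirocumab's residual effect is expected to last 10 weeks, and that the qualifier on unplanned discontinuations shows the authors had planned gaps in mind.

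The qualifier does not carry that weight. It also appears in the main-phase and Cohort 4 formulas, where there is no planned gap, and the written formula still includes the break. The residual effect justifies the 70-day adverse event window. It does not justify exposure, to which the SAP credits only 14 or 28 days after a dose. The convention argument stands in part: a footnote saying that duration includes planned follow-up would make that figure transparent. It would not rescue the mean interval, which is offered as compliance.

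It also stands that the tables are descriptive, that injection counts are reported separately, and that the nominal gap is known, so a careful reader could undo the error.

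A reader might infer more than the documents support:
- **Diluted adverse event rates.** They use time in the combined treatment-emergent period (SAP 2.4.5.1), not this duration, and its 70-day window covers the nominal gap.
- **Biased efficacy or Phase 3 dose choice.** The primary and secondary main-phase analyses stop at the main-phase efficacy period, and SAP 3 rests dose selection on main-phase efficacy. The opposite reading, that no lipid summary is touched, also fails: the combined descriptive lipid table includes the Visit 8 values, though in their own Week 14/16 row.
- **Every patient is affected.** Those who never enter the extension, or who switch at their first extension injection, are not.

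**Conclusion.** The point holds as a minor one. For Cohort 1 to 3 patients with at least one pre-switch extension injection, combined pre-switch exposure is too long by a nominal 8 or 6 weeks, and the mean interval exceeds 14 or 28 days even with perfect dosing. The relative size depends on k, which is unknown, and shrinks as k grows. The patient-year excess of 4.3 to 4.4 is nominal, not a maximum. It rests on full uptake before the switch and an assumed cohort split, and is about 5.2 at the outer edge of the windows.

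Main-phase exposure and compliance, post-switch measures and the incidence of potentially clinically significant abnormalities are unaffected. The on-treatment labelling of Visit 8 values is a small addition.

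**What to change.** 1. **Exposure.** Define combined pre-switch exposure as main-phase exposure plus pre-switch extension exposure, each as last minus first injection in that segment plus 14 or 28 days. The extension term is zero if there is no pre-switch extension injection. For ongoing patients at the first-step analysis, use the cut-off as the last date of the current segment only.
2. **Mean interval.** Divide the sum of within-segment spans by the sum of (n − 1), over segments with at least two injections; set it to missing if there are none. On schedule this gives (42 + 14(k − 1))/(3 + k − 1) = 14 days and (28 + 28(k − 1))/(1 + k − 1) = 28 days. At k = 1 the extension segment drops out, leaving 42/3 = 14 and 28/1 = 28.
3. **On-treatment values.** In the combined last and worst on-treatment summaries, exclude values after the main-phase treatment period (+21 or +35 days) and before the first extension injection, including pre-dose values that day. Label the Week 14/16 lipid row for Cohorts 1 to 3 as off-treatment, pre-dose.

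The cost is SAP wording and small reprogramming, with no new data. Reported exposure falls by a nominal 8 or 6 weeks per affected patient.
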